October 19, 2019

Manuscript title: **Acute effects of High Intensity Interval Training (HIIT) and Steady State Moderate Intensity Training (SSMIT) on Intraocular Pressure among Sedentary Individuals.**

I am pleased to submit the manuscript entitled '*Acute effects of High Intensity Interval Training (HIIT) and Steady State Moderate Intensity Training (SSMIT) on Intraocular Pressure among Sedentary Individuals.*'

Intraocular pressure (IOP) remains the main treatable risk factor for glaucoma, which causes blindness in 4.5 million people worldwide, accounting for slightly more than 12% of all global blindness. Thus, treatment of glaucoma has traditionally been aimed at reducing the IOP, medically or surgically. Exercise is one of the factors that has been proven to influence IOP.

Our study investigated the effects of both forms of aerobic exercise on IOP in sedentary individuals. We believe that our findings would contribute valuable information for the use of exercise in the management of intraocular pressure. In addition, our study also provides useful information for future research on the effect of exercise in glaucoma management.

Sincerely,

DR [name]
Email: [contact]

RESEARCH PROTOCOL

Title of research: Acute effects of High Intensity Interval Training (HIIT) and Steady State Moderate Intensity Training (SSMIT) on Intraocular Pressure among Sedentary Individuals.

Overall the study can be divided into 3 phases :

Phase 1 : Recruitment Phase

Phase 2 : Baseline Assesment Phase

Phase 3 : Exercise Protocol Phase

Phase 1 : Recruitment Phase

1. Application to join the study will be open to all staff of University Malaya Medical Center.
2. 40 participants will be chosen based on the inclusion and exclusion criteria through a randomized method.
3. Consent, Patient Information Sheet and Global Physical Activity Questionnaire will be given and taken.

Inclusion criteria:

1. Healthy volunteers or patients able to undergo different intensity of exercise based on their VO₂max
2. Able to sign informed consent
3. Patients having medical problems to be well-controlled

Exclusion criteria

1. Previous ocular trauma
2. Previous surgery in the eligible eye
3. Known case of glaucoma/glaucoma suspect (IOP > 21mmHg)
4. History of glaucoma laser procedure/surgery within prior 6 months in eligible eye
5. Unable to undergo IOP measurements

6. Unable to give informed consent
7. Undiagnosed visual conditions
8. Uncontrolled medical condition such as:

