 - end stage renal failure
 - uncontrolled diabetes
 - uncontrolled hypertension

Phase 2: Baseline Assessment Phase

Participants will do the assessment in the Sports Medicine Performance Lab

Baseline assessment parameters:

- Blood pressure
- Resting HR
- HRmax
- Body Impedance Analysis (BIA)
- Waist Circumference, Hip Circumference, Height
- VO₂max: 6 minute Astrand Rhythmic cycle ergometer test
- Baseline IOP

*For intraocular pressure assessment, all subjects will be measured at 10am (\pm 1hour) to avoid diurnal variation.

*Subjects are required to avoid any liquid/caffeinated drinks 1 hour prior to IOP measurement.

Phase 3 : Exercise Protocol Phase

[figure not shown]
1. The exercise sessions will be conducted in controlled room temperature (20-23C) between 8.00am to 11.00am using a Monarch 939E Bicycle Ergometer.
2. Participants are not allowed to drink water 2 hours prior until 30 minutes after the exercise session.
3. Each participant will perform both sessions (SSMIT & HIIT) based on the group they were assigned to with a 4 day wash out period between protocols.
4. Each protocol will have the participant cycle for 30 minutes at a speed of 60 rpm.
5. The SSMIT protocol: participants cycle at a moderate intensity of 50% of their VO₂R.

6. The HIIT protocol: consists of 10, 3-minute cycles (1 minute high intensity of 75% VO₂R and 2 minutes low intensity 35% VO₂R).
7. Participants HR will be monitored during the protocols using a HR monitor (Polar Heart Rate Monitor T31-Coded).
8. Before each session, the participants IOP of the right eye will be measured using an iCare rebound tonometer TA01i and repeated IOP measurements will be taken immediately after (0min), 5, 10, 15, 20 & 30 minutes after the exercise session.
9. Each IOP measurement will be taken on the participants right eye with them seated and contralateral eye focused on a distant object.
10. The examiner is blinded to which protocol the participant performed.

Schedule for phase 3:

Week 1: Group A (HIIT) & Group B (SSMIT) : 10 participants/day

Week 2: Group A (CME) & Group B (SSMIT) : 10 participants/day

Statistical Analysis

Data analysis will be conducted using Statistical Package for Social Studies (SPSS) software version 23.

Values for continuous variables are presented as means and standard deviation.

Prior to data analysis normality of continuous variable will be tested using skewness and kurtosis.

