A two-way repeated measure ANOVA will be conducted to evaluate the effect of exercise on IOP and interaction between groups and time followed by using Bonferroni post-hoc test for pairwise comparison.

A paired sample T test will be conducted to assess the difference of IOP levels between interventions. A value of $p < 0.05$ is considered as significant.

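### The paired t-test of HIIT against SSMIT names no time point or summary, states no use of the pre-exercise IOP and has no multiplicity rule; the family for the ANOVA's Bonferroni is also unstated

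*Combined protocol and SAP*

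**What the plan says.** Phase 3, item 8 sets the measurements. "Before each session, the participants IOP of the right eye will be measured", and then "repeated IOP measurements will be taken immediately after (0min), 5, 10, 15, 20 & 30 minutes after the exercise session". That is seven IOP values per session. Under item 3 every participant does both sessions, so pairing is by participant. Phase 1, item 2 sets the number: "40 participants will be chosen based on the inclusion and exclusion criteria".

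The Statistical Analysis section plans two analyses of IOP:

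- A two-way repeated-measures ANOVA to "evaluate the effect of exercise on IOP and interaction between groups and time", "followed by using Bonferroni post-hoc test for pairwise comparison".
- In a separate sentence: "A paired sample T test will be conducted to assess the difference of IOP levels between interventions". The only threshold that follows is p<0.05.

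No primary endpoint is named, and neither analysis is ranked above the other.

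**The concern.** A paired t-test needs one number per person per session. The plan collects seven and does not say which one, or which combination, enters the test. The wording fits a single test on a mean, a test at each of the six post-exercise times, or a time picked after the results are known. A reader of the eventual report could not tell whether p<0.05 came from one planned test or was the best of several.

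The comparison of the two protocols is the question in the study's title, and this sentence is the plan's most direct test of it.

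The pre-exercise reading is a separate matter. A test on raw post-exercise values carries any chance difference in starting IOP between the two sessions into the result. The reading needed to remove that difference is already taken, but the plan does not say whether the t-test uses it.

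**Working it through.** **Inputs from the documents.** 40 participants (Phase 1, item 2), each doing both sessions (Phase 3, item 3), so n = 40 paired differences; six post-exercise times (Phase 3, item 8); significance at 0.05, taken as two-sided because the sidedness is not stated. The plan gives no power, effect size or SD, so there is no planned figure to reproduce.

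**Assumptions, not in the documents.** The correlation between HIIT-minus-SSMIT differences at different times; the correlation between the paired pre-exercise and paired post-exercise differences; the effect sizes, in units of the SD of the paired difference.

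**1. Error rate if all six times are tested and any p<0.05 counts.** For independent times it is 1 − 0.95^6 = 0.265. For correlated times it was simulated with no true difference, n = 40 and a common correlation between times:

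| Correlation between times | Any of six p<0.05 | Any of six p<0.05/6 |
|---|---|---|
| 0 | 26.5% | 5.0% |
| 0.5 | 21% | 4.3% |
| 0.8 | 14% | 2.9% |
| 0.95 | 9% | 1.8% |
| 0.99 | 7% | 1.3% |

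One test on one named quantity has a 5% error rate.

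**2. What the Bonferroni could cover.** The per-comparison threshold is 0.05/m.

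- HIIT against SSMIT at the six times: 0.05/6 = 0.0083. An adjusted protocol comparison would then already exist, and the t-test would repeat it at a looser threshold.
- HIIT against SSMIT within each time separately: m = 1, so nothing is adjusted across times.
- All pairs of the 14 session-by-time cells: 14 × 13/2 = 91 comparisons, 0.05/91 = 0.00055.

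The text does not choose among these.

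**3. Gain from the pre-exercise reading.** Regress the paired post-exercise difference on the paired pre-exercise difference and test the intercept. The residual variance is (1 − r²) times the raw variance, where r is the correlation between the two differences. For a 0.4 SD difference and 40 pairs, the raw test has noncentrality 0.4 × √40 = 2.53 and power 69%. Adjusted power, simulated on 38 degrees of freedom:

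| Assumed r | 1 − r² | Adjusted power |
|---|---|---|
| 0 | 1.00 | 68% |
| 0.3 | 0.91 | 72% |
| 0.5 | 0.75 | 80% |
| 0.7 | 0.51 | 93% |

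Overall error is 5% with or without adjustment.

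**4. Price of adjusting for six times.** For a 0.5 SD difference at one time the noncentrality is 0.5 × √40 = 3.16 on 39 degrees of freedom. Power is 87% at 0.05 and 65% at 0.05/6.

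**The case against.** *It may be one test.* The sentence is in the singular and can mean a single t-test at 5%. That stands. A reader might infer from the table that the plan has a 26% false-positive rate. The documents do not support this: the figure needs six tests, any of which counts, and independent times.

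*The ANOVA may already deal with baseline.* An effect of exercise on IOP most naturally needs the pre-exercise reading as a level of time. If *groups* means the two protocols, the interaction would then compare changes from pre-exercise. A reader might therefore go too far in concluding that the plan discards the baseline; the text is only silent. That silence still leaves the t-test undefined.

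*The ANOVA may not be a second test of the protocols.* Phase 3 uses Group A and Group B for the assigned groups, so *groups* in the ANOVA could mean those. It would be too strong to say that the plan certainly holds two unranked tests of HIIT against SSMIT. The text settles neither meaning.

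*The 40 pairs are not secure.* The Phase 3 schedule gives Group B SSMIT in both weeks, and Group A an undefined CME in week 2. That contradicts item 3. If only 20 pairs existed (assuming equal groups), raw power at 0.4 SD would be about 40% instead of 69%.

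*A named outcome alone would cure the ambiguity.* True: a paired t-test on one stated mean or change score is also a single 5% test. The regression is proposed for its precision; validity does not depend on it.

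**Conclusion.** The concern holds as a gap in specification, and the plan should be changed on this point. The t-test lacks a time point or summary, a stated role for the pre-exercise IOP, and a multiplicity rule; the Bonferroni family for the ANOVA follow-up is also missing. The consequence ranges from none (one test, 5%) to an error rate of about 7% to 26% if all six times are tested and any counts, depending on a correlation that the documents do not give. The benefit of baseline adjustment likewise depends on an assumed correlation: from a loss of about 1 point of power to a gain of about 24 points (69% to 93%). All these figures assume 40 complete pairs under Phase 3, item 3.

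Nothing in the documents shows that a time point was picked after the results were seen. However, the cover letter submits a manuscript and says "Our study investigated the effects of both forms of aerobic exercise on IOP in sedentary individuals", so a choice made now may not be prospective.

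**What to change.** 1. Name one primary HIIT-minus-SSMIT contrast: mean post-exercise IOP over the six readings, or one pre-named time if a short-lived difference is expected. Test it once at two-sided 0.05.
2. Estimate it by regressing the paired post-exercise difference on the paired pre-exercise difference, with a term for sequence (Group A or B) centred so that the intercept is the protocol effect averaged over the two sequences.
3. Report the six time-specific contrasts as secondary, with Holm, or with Bonferroni and the six times named as the family.
4. State whether pre-exercise IOP is a level of time in the ANOVA, what *groups* means there, and which comparisons its post-hoc covers.
5. Reconcile the Phase 3 schedule with item 3, since the number of pairs depends on it.
6. If data have already been seen, label the choice as not prospective and show all six adjusted contrasts with equal prominence.

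**Cost.** Wording and one regression on readings already planned. Adjustment costs about 1 point of power if pre- and post-exercise differences are uncorrelated. Sequence uses one degree of freedom (38 to 37); it can repay this if there is a period effect. With an assumed shift of ±0.5 SD, r = 0.5 and a 20/20 split, power was about 70% without the term and 81% with it.

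An effect at a single time becomes harder to declare among the secondary contrasts (65% against 87% for 0.5 SD). A six-reading mean dilutes such an effect: power is roughly 8% to 12.5% for 0.5 SD at 0 min only, against 88% to 99.8% if it lasts through all six times, for assumed correlations between times of 0.95 down to 0.3. The choice in step 1 should therefore follow the expected time course.
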